1. SUMMARY

A pilot controlled clinical study is proposed to evaluate and compare the degree of satisfaction and skin comfort with cosmetic creams PB-011 and PB-012 in oncology patients who have developed palmar and plantar peripheral poly-neuropathy due to treatment with chemotherapy or chemotherapeutic agents fused to monoclonal antibodies (immunocytostatic). Both products are cosmetic creams derived from the line Nocisens (for the care of sensitive skin with atopic tendency). The hypothesis to be tested is that care with PB-011 or PB-012 for sensitive skin associated with palmar and plantar peripheral poly-neuropathy in oncology patients will increase their degree of satisfaction and skin comfort. A parallel, randomised, double-blind, masked, double-blind study is proposed in patients who are about to start chemotherapeutic treatment. The study involves two populations: (i) the population where PB-011 cream will be tested; and, (ii) the population that will test PB-012 cream. The duration of the project will be 12 months, and participants will have to apply the cream on their hands once a day during the period of chemotherapy treatment. A sample size of 60 volunteers per population has been estimated to ensure statistical significance. As a relevant qualitative variable for patients who have developed neuropathy, the degree of satisfaction and skin comfort will be assessed by means of a questionnaire.

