2.3. Description of the products under study

Product: Cosmetic creams with Ref. PB-011 and PB-012

Trade name: Nocisens. The formulation with the best acceptance in the study population will be marketed under the name Oncapsisens.

Commercial name: Prospera Biotech S.L

Code and INCI:

- PB-011: Capric Triglyceride, Glyceryl Behenate, Glyceryl Stearate, Hydrogenated Castor Oil, Diethylene Glycol Monoethyl Ether, Tocopherol, Hydroxymethoxyiodobenzyl Glycolamide Perlargonate.
- PB-012: Capric Triglyceride, Glyceryl Behenate, Glyceryl Stearate, Hydrogenated Castor Oil, Diethylene Glycol Monoethyl Ether, Tocopherol.

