4. JUSTIFICATION AND STUDY OBJECTIVES

The toxicity generated during chemotherapy treatments can usually produce skin discomfort or peripheral polyneuropathy. CIPN manifests itself above all in the extremities, mainly in the palmar and plantar regions, giving rise to uncomfortable sensations such as itching, numbness, tingling, pain or dryness, i.e. skin sensitivity. Currently, there is no specific treatment to combat this skin sensitivity and oncology specialists recommend keeping the skin hydrated through the use of cosmetic creams.

Taking into account that these sensations imply a deterioration in the quality of life of patients, our hypothesis is that cosmetic creams for sensitive skin with references PB011 and PB012 could improve comfort and the degree of satisfaction of cancer patients with CIPN. The reason for this hypothesis is that cosmetic creams contain ingredients that reinforce the barrier function of the epidermis and improve the hydration and appearance of the skin. The study has been designed to define which of the two creams produces greater satisfaction in patients.

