6.3. Expected number of subjects and justification

A total of 120 volunteers diagnosed with any type of cancer, in stages I-III, who are about to start or have received a maximum of 1 dose of chemotherapy treatment will be studied.

Two study populations are contemplated: (i) population that will receive the PB-011 cream; (ii) population that will receive the PB-012 cream. Both populations will apply the cream on their hands once a day. If sensory discomfort or, in the worst case, peripheral neuropathy appear during the chemotherapy treatment period, the application will be increased to twice daily on the affected areas (generally hands and feet).

The number of volunteers for the study is 60 for each population. This value is based on: (i) a difference of 2 points between both populations (PB-011 and PB-012), on a satisfaction scale of

0 to 10 points, with 0 being very dissatisfied and 10 very satisfied, or 2 points on the Von Frey scale; (ii) a variability (standard deviation) of 3 points in each population; (iii) a p-value of statistical significance <0.05 and, (iv) a probability of finding a statistically significant difference for the p-value <0.05 of 95%.

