7. PRODUCT DESCRIPTION

7.1. Product

Subjects who meet the inclusion/exclusion criteria and who become part of the study may take any medication that their physician deems appropriate, excluding those specified in the exclusion criteria.

Patients participating in the study will apply:

Cosmetic creams Ref. PB-011 and PB-012.

Tradename: Nocisens.

Business owner: Prospera Biotech S.L.

Composition:

- PB-011: Capric Triglyceride, Glyceryl Behenate, Glyceryl Stearate, Hydrogenated Castor Oil, Diethylene Glycol Monoethyl Ether, Tocopherol, Hydroxymethoxyiodobenzyl Glycolamide Perlargonate.
- PB-012: Capric Triglyceride, Glyceryl Behenate, Glyceryl Stearate, Hydrogenated Castor Oil, Diethylene Glycol Monoethyl Ether, Tocopherol.

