12. STATISTICAL ANALYSES

The analysis of the results of this study will be approached from two perspectives. On the one hand, the modified intention-to-treat (MITT) population will be analyzed, which corresponds to all those subjects who have used the product at least once and for whom satisfaction data is available. On the other hand, a per-protocol analysis will be carried out in which all randomized subjects who have followed the study instructions until the end of the study will be included.

The clinical evaluation data may be analyzed as quantitative or qualitative variables. In the first case, the results will be expressed as mean \pm standard deviation, minimum and maximum. In the case of qualitative variables, the results will be expressed as frequency and percentage. For all the parameters to be measured (both clinical variables and responses to questionnaires) there will be a baseline measurement taken before the start of the protocol that will serve as a control measurement. The change in the main variable (degree of satisfaction) will be analyzed

using the paired Student's T test. The change in the secondary variables will be studied according to their nature (qualitative or quantitative variables) and applying the corresponding test in each case: Chi square, Student's T, ANOVA, Kruskal-Wallis or Mann-Whitney U. The impact of each variable on the main variable will be assessed, especially the impact of treatment, diagnosis, age and gender.

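### The hypothesis that either cream raises satisfaction, tested by paired change from baseline, is one the two-cream design cannot answer; hypothesis and primary test should be PB-011 versus PB-012

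*Combined protocol and SAP*

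**What the plan says.** Section 1 opens its hypothesis with "The hypothesis to be tested is that care with PB-011 or PB-012 for sensitive skin" and predicts that such care "will increase their degree of satisfaction and skin comfort". No comparator is named. Section 4 repeats the idea for both products, which "could improve comfort and the degree of satisfaction of cancer patients with CIPN".

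The same section 4 then sets a different question: "The study has been designed to define which of the two creams produces greater satisfaction in patients". Section 6 also plans to compare the two groups after treatment, among patients who developed neuropathy. Section 6.3 sizes the trial on a 2-point difference between the creams. Section 2.3 attaches a decision to that comparison: "The formulation with the best acceptance in the study population will be marketed under the name Oncapsisens".

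On the arms, section 6.3 states: "Two study populations are contemplated: (i) population that will receive the PB-011 cream; (ii) population that will receive the PB-012 cream". There is no untreated, usual-care or other-emollient group.

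On the analysis, section 12 makes each patient's baseline the control. "The change in the main variable (degree of satisfaction) will be analyzed" with a paired Student's t test, the only test named for that variable. Section 12 adds that the impact of treatment, diagnosis, age and gender on the main variable will be assessed, but gives no model and does not say whether treatment means the cream or the chemotherapy.

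**The concern.** The hypothesis and the named test both ask whether patients change from baseline. Between the two measurements much happens besides cream use. Patients enter with at most one chemotherapy session behind them (6.1) and without pre-existing neuropathy unrelated to chemotherapy (6.2). They then go through the full course and are assessed at its end if discomfort has developed (7.2, 8.2). Application frequency also rises once discomfort appears (2.7, 6.3). No group goes through the same interval without a cream, so nothing separates a cream effect from the rest.

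The bias can run either way. Because the end assessment follows the onset of discomfort, worsening is the likelier drift, and it could mask a real benefit. A favourable drift would look like a benefit from both creams. If section 12 is followed as written, the headline result is a change that cannot be interpreted, and the randomised comparison has no named test.

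**Working it through.** **1. What the sample size was built for.** Inputs from section 6.3: difference 2 points between the creams, SD 3 in each population, significance level 0.05, power 95%. Sidedness is not stated; two-sided is assumed. For two independent means:

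n per arm = 2 × (1.960 + 1.645)² × 3² / 2² = 58.5, so 59.

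The t-distribution version gives 59.5, so 60, with power 95.2% at 60 per arm. The one-sided version gives 49. The stated 60 is therefore reproduced as a two-sided, two-sample comparison. A paired calculation would need an SD of change, which section 6.3 does not give.

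**2. What each analysis identifies.**

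| Contrast | Differs between the things compared | Can answer |
|---|---|---|
| End versus baseline, within an arm | Cream, chemotherapy, onset of discomfort, application frequency, time | Whether scores changed, not why |
| PB-011 versus PB-012, randomised | Formulation | Which cream does better |

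**3. Illustration of the paired test.** Suppose neither cream has any effect and both arms shift by the same amount for other reasons. The documents give no drift size, no baseline-to-end correlation r and no SD of change, so all three are assumptions. The per-arm SD of 3 is borrowed from section 6.3, where it belongs to a 0 to 10 satisfaction scale and not to the DLQI.

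SD of change = 3 × √(2(1 − r)), which is 4.24, 3.00 and 1.90 for r = 0, 0.5 and 0.8.

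Noncentrality for a 1-point shift with n = 60 is √60 / SD of change: 1.83, 2.58 and 4.08. Against the two-sided 5% critical value of 2.00 (59 degrees of freedom), the chance of significance in one arm is:

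| Shared shift | r = 0 | r = 0.5 | r = 0.8 |
|---|---|---|---|
| 0.5 points | 15% | 25% | 52% |
| 1.0 point | 44% | 72% | 98% |
| 1.5 points | 77% | 97% | >99% |

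A between-arm test is unaffected by a shift common to both arms and stays at 5% throughout.

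**4. Direction.** The table counts significance in the direction of the drift. If the 1-point drift is adverse, the chance of a significant favourable change is under 0.01% at all three correlations. The percentages are false confirmations of the stated hypothesis only when the drift is favourable.

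**5. Setting two paired p-values side by side is no substitute.** With identical creams and a 1-point shift, exactly one arm is significant with probability 2p(1 − p): 2 × 0.435 × 0.565 = 49% at r = 0, 2 × 0.719 × 0.281 = 40% at r = 0.5, and 2 × 0.980 × 0.020 = 4% at r = 0.8. At low to moderate correlation, that reading would often pick a winner between equal products.

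**The case against.** The strongest reply is that the comparative aim is already in the protocol: in the opening sentence of section 1, in the introduction, and in sections 4, 6 and 6.3. On that view the hypothesis sentence is loose drafting, and the impact of treatment in section 12 covers the comparison. The first part stands: a reader might infer that the trial has no comparative purpose, and that would be wrong. The second does not, because an undefined impact assessment is not a primary test, and the test that is named is a within-patient one.

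A reader might also infer that the sponsor intends to claim benefit from a within-arm change. No section says so; the stated use of the result, in section 2.3, is comparative. The risk lies in a hypothesis and a test that invite such a claim, not in an announced one.

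It is tempting to say that the comparison isolates the one ingredient on the PB-011 list that PB-012 lacks ("Tocopherol, Hydroxymethoxyiodobenzyl Glycolamide Perlargonate" ends the former; the latter stops at tocopherol). The documents do not support this. Section 3 says that the formulations also differ slightly in texture and properties, and the lists give no proportions.

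Finally, the size of the illustration is open to challenge, fairly. Drift, correlation and SD of change are all assumed, and a single figure such as 72% would be too narrow. Calling the study a pilot is a weaker defence, since section 1 states a hypothesis to be tested and a sample size meant to secure statistical significance.

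**Conclusion.** The point holds. As written, the plan tests a change that chemotherapy and time confound, while the randomisation and the sample size answer a different question. That conclusion rests on the arms, the timing of assessment and the named test, and does not depend on the illustrative figures. Those show only that the problem can be large: 44% to 98% of arms significant for a 1-point shared shift, against 5% for a between-arm test. They should not be read as false-positive rates for the hypothesis, because worsening is the likelier drift and would tend to hide a benefit.

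It would go too far to conclude that the trial is uninformative or must have a third arm. PB-011 versus PB-012 is a valid randomised question. A no-cream or usual-care arm would be needed only to keep the claim that the creams improve satisfaction. If both creams help equally, this design cannot show it.

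**What to change.** - **Sections 1 and 4:** restate the hypothesis as a difference between PB-011 and PB-012 in the main variable at the end of chemotherapy. Describe it as a contrast between two formulations, not as the effect of a single ingredient.
- **Section 12, primary analysis:** replace the paired t test with a between-arm comparison, for example ANCOVA of the end-of-chemotherapy score on arm and baseline. Section 12 already plans the baseline measurement.
- **Section 12, interpretation:** state that within-arm change is descriptive only, and that neither it nor a non-significant between-arm difference will be used to claim that the creams improve satisfaction.

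The cost is wording in three sections and a changed primary test. No arm, visit or measurement is added, and the calculation behind 60 per arm still applies if all 60 contribute. Two neighbouring matters should be settled in the same edit: whether the comparison covers all patients or only those with neuropathy (section 6), and whether the 2-point difference and SD of 3, set on a 0 to 10 scale in section 6.3, apply to the DLQI named in section 8.1. The downside is that the sponsor gives up a benefit claim that the design cannot support.

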2. GENERAL INFORMATION

2.1. Study identification

Study code: 20PB-02

Study title: 'Study for the evaluation of the degree of skin satisfaction of the cosmetic creams for sensitive skin PB-011 and PB-012 in oncology patients with palmoplantar polyneuropathy secondary to treatment with chemotherapy or chemotherapeutic agents fused to monoclonal antibodies (immunocytostatic)'.

2.2. Type of study

Multicentre, controlled, parallel, randomised, double-blind, masked, double-blind, randomised study.

2.3. Description of the products under study

Product: Cosmetic creams with Ref. PB-011 and PB-012

Trade name: Nocisens. The formulation with the best acceptance in the study population will be marketed under the name Oncapsisens.

Commercial name: Prospera Biotech S.L

Code and INCI:

- PB-011: Capric Triglyceride, Glyceryl Behenate, Glyceryl Stearate, Hydrogenated Castor Oil, Diethylene Glycol Monoethyl Ether, Tocopherol, Hydroxymethoxyiodobenzyl Glycolamide Perlargonate.
- PB-012: Capric Triglyceride, Glyceryl Behenate, Glyceryl Stearate, Hydrogenated Castor Oil, Diethylene Glycol Monoethyl Ether, Tocopherol.

2.7. Expected duration of the study

The overall duration of the study is expected to be 12 months from the start of recruitment of the populations until the last follow-up control and analysis of the data generated.

The intervention (application of the cosmetic cream) will take place from the beginning to the end of the chemotherapy treatment, with 1 daily application of the product (PB-011 or PB-012) on the hands. If sensory discomfort or, in the worst case, peripheral neuropathy develops during the period of chemotherapy or immunocytostatic treatment, the application shall be increased to twice daily on the affected areas (usually hands and feet). In case of lack of efficacy of the product, the investigator in charge may withdraw the subject from the study after three months of application of the product.

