The Institute for Research, Development and Innovation in Health Biotechnology of the Miguel [name] University of Elche (IDIBE-UMH) has been studying the mechanisms that govern skin imbalances for many years. This knowledge has been transferred to Prospera Biotech, and has been used to develop a line of creams for sensitive skin (trade name Nocisens). The mixture of fatty acids, tocopherol and innovative cosmetic ingredients means that Nocisens has a dual action on the stratum corneum. On the one hand, it strengthens the skin's barrier function by preventing water loss, which helps to increase hydration and re-establish the skin's protective function and, on the other hand, it prevents the accumulation of reactive oxygen species in the cells, protecting the skin from their harmful effects. These two actions help Nocisens cosmetic cream to create a feeling of well-being and comfort for the skin.

However, in cosmetics, the degree of acceptance of a product is a key element for adherence to treatment. We have therefore developed two formulations derived from Nocisens, PB-011 and PB-012, with slightly different texture, composition and properties in order to adapt them to the needs of the sensitive skin characteristic of palmo-plantar neuropathy mediated by chemotherapeutics.

Given that PN induced by treatments with chemotherapy or chemotherapeutic agents fused to monoclonal antibodies (immunocytostatic) is characterised by skin imbalances that affect the quality of life of the people who suffer from it, a parallel, randomised, double-blind, masked study is proposed in patients who are about to begin oncological treatment to compare the

degree of acceptance of PB-011 and PB-012 cosmetic creams in this population. The study involves two populations: (i) the population where PB-011 cream will be tested; and, (ii) the population that will test PB-012 cream. The duration of the project will be 12 months, and participants will have to apply the cream once a day on their hands during the period of chemotherapy treatment. A sample size of 60 volunteers per population has been estimated to ensure statistical significance. As a relevant variable for the patients, the degree of skin satisfaction will be assessed every fortnight by means of a questionnaire only in the case of discomfort in the hands and/or feet.

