7.2. Study development

When a subject meets all the inclusion criteria and none of the exclusion criteria and has signed the informed consent document, he/she is electable to enter the study. The researchers will collect the data of each volunteer and notify Prospera Biotech of their inclusion. Patients will

receive the cream when they start the chemotherapy treatment. Creams will be either sent directly to the participants' home or sent in advance to the centers and stored there at room temperature (15-25°C) until distributed to participants. The principal investigator will create the Data Notebook for each subject, anonymizing the personal and clinical data in all cases. The type of product to be assigned will be determined by the randomization procedure.

Subjects taking part in the study should apply a sufficient amount of cream to their hands once a day for the duration of their chemotherapy treatment. Those subjects who develop skin sensitivity or peripheral neuropathy should undergo the following procedures:

1. Increase the frequency of use of the cream to twice a day in all affected areas.
2. Once the chemotherapy treatment is finished: evaluation of the degree of skin satisfaction by means of a questionnaire that assesses the Dermatology Life Quality Index [DLQI] (Annex II) and the degree of satisfaction with the cream (Annex IV). Evaluation of the discomfort generated by peripheral neuropathy through a follow-up questionnaire (Annex III). Measurement of skin sensitivity using Von Frey hairs for patients who voluntarily wish to do so. These procedures will be carried out by the study collaborators of each center. In case of need, Prospera Biotech team could also contribute to make the follow-up (questionnaires) telematically.

The study procedures are included in section 8.2.

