7.3. Withdrawal criteria

Based on the provisions of the Declaration of Helsinki, the subjects have the right to withdraw from the study at any time and for any reason, being able to express it personally or through their representative. The investigator reserves the right to withdraw any subject from the study in the following cases:

- Subject abandonment: violation of inclusion or exclusion criteria or non-cooperation. In case of withdrawal, the reason is reflected in the Data Notebook.
- By efficacy criteria: if, in the investigator's opinion, the product is not causing any benefit to the subject under study.
- Due to safety criteria: in the event of a serious or unexpected adverse event and that, for this reason, or due to the medication that may be instituted to reverse such event, it is considered that its continuation in the study is not pertinent.

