8.2. Collection of variables

The main variable, degree of skin satisfaction/comfort, will be evaluated using the DLQI^{12, 13} questionnaire available in ANNEX II.

Mechanical sensitivity will be assessed by means of the Von Frey filament test in patients who voluntarily want to undergo it. The pain threshold and mechanical allodynia of patients with post-chemotherapy polyneuropathy will be measured before starting the study and once the chemotherapy treatment is over, expressing the threshold in the minimum number of pressure units that trigger pain in patients with the corresponding filament. of Von Frey approved.

The follow-up of the patients will be carried out through the usual oncological control during treatment. If the patients develop sensory or skin discomfort during this period, at the end of the treatment a check-up will be carried out using the following questionnaires:

- Follow-up of discomfort sensations available in a questionnaire derived from the Leonard Scale (ANNEX III).
- Degree of skin satisfaction by means of the Dermatology Life Quality Index [DLQI] (Annex II).
- Degree of satisfaction with the cream (Annex IV).

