ANNEX I: DATA NOTEBOOK

See attached document

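### Withdrawal for lack of benefit ends study participation with no outcome assessment described, so outcomes can be lost for a reason related to the outcome

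*Combined protocol and SAP*

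**What the plan says.** Two sections allow withdrawal for lack of benefit. Section 2.7 says that "the investigator in charge may withdraw the subject from the study after three months of application of the product". Section 7.3 allows it if, in the investigator's opinion, "the product is not causing any benefit to the subject under study", with no minimum time. Both remove the patient from the study, not only from the cream.

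On what is recorded, section 7.3 says, within its item on abandonment: "In case of withdrawal, the reason is reflected in the Data Notebook". The notebook itself ("ANNEX I: DATA NOTEBOOK") is an attachment that is not shown.

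On outcome timing, section 7.2 reads "Once the chemotherapy treatment is finished: evaluation of the degree of skin satisfaction by means of a questionnaire", for subjects who have developed skin sensitivity or neuropathy. Section 8.2 agrees: for patients with discomfort, "at the end of the treatment a check-up will be carried out using the following questionnaires". The introduction alone mentions a denser schedule, in which satisfaction "will be assessed every fortnight by means of a questionnaire only in the case of discomfort in the hands and/or feet". Sections 7.2, 8.2 and 12 do not take this up.

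On analysis, section 12 defines MITT as "all those subjects who have used the product at least once and for whom satisfaction data is available". Per-protocol requires following the instructions to the end of the study. Change in the main variable is tested with a paired t test against a baseline taken before the start. No method for missing data is given.

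**The concern.** Read together, these rules let a patient leave because the cream seemed not to work and then have no post-baseline score. That patient leaves the per-protocol set. The patient also leaves MITT, unless some satisfaction data happen to exist. A patient with only a baseline score cannot enter a paired test, however MITT is read.

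This is loss related to the outcome, not random loss. The summary's hypothesis is that care with either cream will increase satisfaction, and the named test measures change. If the poorer responders are missing, the mean change in each arm looks better than it is. Section 4 also asks which cream satisfies patients more, and a true difference tends to shrink if more patients are lost from the worse arm. Scores that were not collected cannot be recovered at analysis.

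**Working it through.** **The plan's own figure.** Section 6.3 gives a difference of 2, SD 3, significance level 0.05 and power 95%. Taken as two-sided, n = 2(1.960 + 1.645)² × 3² / 2² = 2 × 12.996 × 2.25 = 58.5, so 59 per arm; the exact t calculation gives 60. The stated 60 per arm reproduces, and no allowance for loss is among its inputs.

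**What follows from the text for a patient withdrawn before chemotherapy ends.**
- Baseline: taken (section 12).
- At withdrawal: the reason is recorded; no questionnaire is described.
- After withdrawal: the only follow-up described that is not tied to the end of treatment is for adverse events (section 9.1).
- End-of-chemotherapy questionnaires: not described for someone who has left the study.

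**Illustration of size.** It uses the 0-10 scale of section 6.3, not DLQI units. From the plan: difference 2, SD 3. Assumed, because the plan gives no values: loss p of 10%, 20% or 30%; correlation r of 0.3 or 0.5 between the investigator's judgement and the score; normal scores; a change SD of 3.

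*Within an arm.* If the lowest fraction p on the judgement is lost, the mean of those retained rises by r × 3 × φ(z_p)/(1−p). The ratio φ(z_p)/(1−p) is 0.1755/0.9 = 0.1950, 0.27996/0.8 = 0.34995 and 0.3477/0.7 = 0.4967.

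| r | 10% lost | 20% lost | 30% lost |
|---|---|---|---|
| 0.3 | 0.18 | 0.31 | 0.45 |
| 0.5 | 0.29 | 0.52 | 0.75 |

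*Chance of a significant improvement when there is none* (two-sided paired t test at 0.05; simulation, 20,000 runs per setting; 2.5% without loss). With a true change of zero:

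| r | Assessed per arm before loss | 10% lost | 20% lost | 30% lost |
|---|---|---|---|---|
| 0.3 | 20 | 4.4% | 6.0% | 7.4% |
| 0.3 | 60 | 6.2% | 10.9% | 16.3% |
| 0.5 | 20 | 6.1% | 9.9% | 14.4% |
| 0.5 | 60 | 11.0% | 24.2% | 38.9% |

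At r = 0 the rate stays at 2.3-2.7%, so the excess comes from selection, not from smaller numbers. With a true worsening of 0.5 points, the settings above give from under 1% to about 8%. With a true worsening of 1 point they give 0 to about 1.3%.

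*Between creams.* True means are 2 and 0. A common judgement threshold removes p of the worse arm. If the arm affects the judgement only through the score, the judgement shifts between arms by r × 2/3, and the better arm loses Φ(z_p − r × 2/3). The observed difference is 2 plus the better arm's rise minus the worse arm's rise.
- r = 0.3: the better arm loses 6.9%, 14.9% or 23.4%; the difference is 1.95, 1.93 or 1.91.
- r = 0.5: the better arm loses 5.3%, 12.0% or 19.6%; the difference is 1.88, 1.82 or 1.77.

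**The case against.** Several points on the other side have force.

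- **Data before withdrawal may exist.** Patients judged to have no benefit are plausibly those with discomfort, so the fortnightly questionnaires could have produced scores, and MITT asks only that satisfaction data be available. This could soften the loss. But the schedule is missing from the operative sections, and section 12 does not say how such scores would be used. An exit form in the Data Notebook cannot be excluded either, so it would go too far to infer that these outcomes are certain to be lost.
- **The frequency is unknown.** Withdrawal is discretionary, and no rate or chemotherapy duration is given. Under section 2.7 alone, only patients whose chemotherapy runs beyond three months are exposed; section 7.3 has no such limit. The 10-30% range is an assumption.
- **False claims of improvement.** A reader might infer that the trial is likely to report a false improvement, with a chance of up to 39%. The documents do not support that. The figure needs a true change of exactly zero and 60 assessed patients per arm, and 60 is not assured because only those who develop discomfort are followed up. Patients enter before chemotherapy or after at most one session, so worsening from baseline is plausible. The upward shift in mean change remains, but it would then understate worsening.
- **The comparison of creams.** A reader might infer a large distortion. A difference as low as 1.18 does arise in the same model, but only if 30% of the worse arm is lost and the judgement tracks the score exactly. A reader might equally infer that equal creams can never give a false difference. That holds only if the withdrawal threshold is the same for both codes. Investigators are blind to the product but see the A/B code (section 5.3), so a common threshold is reasonable but not guaranteed.

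**Conclusion.** The concern stands in a limited form. As written, the plan allows outcomes to be lost because of the outcome, and the visible text has nothing that reliably prevents or repairs it. The real loss cannot be sized from the documents.

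Under the assumed 10-30% loss and correlation of 0.3-0.5, mean change within an arm is overstated by about 0.2 to 0.75 points on a 0-10 scale. Improvement is then overstated or worsening understated. The chance of a false improvement rises from 2.5% to 4-39% only if the true change is zero; with a true worsening of 1 point it stays at about 1% or less. Between creams, a true difference of 2 shrinks modestly, to about 1.95-1.77, if the judgement reflects the arm only through the score. If the creams are equal and the threshold is common to both codes, no false difference arises. The gap should be closed because closing it is cheap, not because a wrong conclusion has been shown to be likely.

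**What to change.** - In sections 2.7 and 7.3, let lack of benefit stop the cream, not study participation, and carry the three-month condition into 7.3. The patient's own right to leave the study is unchanged.
- Collect the DLQI and Annex IV when the cream is stopped, and the DLQI again at the end of chemotherapy, remotely if needed, as section 7.2 already allows. Repeating Annex IV at the end adds little, since it asks about a cream no longer in use.
- In section 12, keep these patients in MITT and state in advance which score is primary. The end-of-chemotherapy score is suggested, with the score at stopping as a sensitivity analysis. The choice depends on the question asked: the score at stopping is arguably closer to acceptance of the cream.
- Report lack-of-benefit stops by arm.

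The cost is a few sentences and one extra use of existing questionnaires. The small downside is a little more follow-up of patients who have stopped the cream.
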